9.2 Sample Size and Randomization

Power and sample size estimate: We assume that dropout will be at 10% and 20% at the end of 12 week treatment phase and 6 and 12 month follow-up, respectively. For Aim 1, if the treatment main effects are linear over the 12 week treatment phase on HAMD, our design with 7 time points (baseline, 2, 4, 6, 8, 10, 12 weeks) and with complete data on 99 subjects within each arm (10% dropout) will have 80% power at significance level $\alpha=0.05$ for detecting a treatment and time interaction corresponding to no difference at baseline and a difference of $d = 0.32$ SDs between any two arm at the end follow-up. Our R21 project found an effect size of 0.65 in HAMD between TCC and HEW at 12 weeks. If treatment effects continue to grow linearly over the 6 and

12 month follow-up, our design with complete data on 88 subjects within each arm (20% dropout) will have 80% power at significance level $\alpha=0.05$ for detecting a group difference between any two arms of $d = 0.36$ SDs at 6 and 12 month follow-up. The reported power is based on number of subjects with complete data, and hence is a conservative estimate of the actual power of our design, since the proposed GLMM framework utilizes all observed data collected from all subjects. In addition, the reported power analysis is based on a correlation of 0.5 between measurements obtained at different time points. Selection of the covariance structures within the GLMM model will be based on likelihood ratio test and/or AIC (Akaike Information Criterion). If we find either significant interactions or main effects, follow-up contrasts will be used to determine at which time points there has been significant change and/or differences in treatment effects relative to baseline.

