9.4 Interim Analyses and Stopping Rules

We will not conduct interim analyses on primary outcomes.

- If a patient demonstrates worsening of their depressive symptoms by week 12 (i.e., CGI-I score > 4) of treatment, they will be discontinued from the study and referred for appropriate clinical services.
- Suicidal ideations with the HAMD item 3 score of 3 or greater
- Other SAEs.
- Engagement in alternative treatments interfering with the primary outcomes of the interventions

All dropouts will be analyzed by the reason for termination and the reasons will be classified as:

- a) Lack of efficacy; b) Side-effects; c) Lost-to-follow up; d) Hospitalization; e) Death; f) Other
- Relation to the study interventions: a) likely; b) probable; c) unlikely.

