9.6 Data Analyses

Statistical Analysis Plan.

The study will include 220 subjects assigned to TCC/HEW in a 1:1 ratio, within each treatment arm. Prior to performing the primary analyses, descriptive statistics and graphical summaries will be obtained for the primary outcomes (HAMD-24 (Aim 1), connectivity in DMN in rs-fMRI and BOLD activation during the mood task in the anterior cingulate (Aim 2)) to check for outliers and violations of model assumptions and to assess the need for transformations or non-parametric methods. We will also plot each of the primary measures as a function of time to examine the form of the longitudinal trajectories. (HAMD-24 scores will be recorded every 2 weeks throughout the intervention.) Longitudinal analysis proposed will rely on generalized linear mixed models (GLMMs). GLMMs properly account for correlations induced by repeated measurements within subjects, allow for both fixed and time-varying covariates and automatically handle missing data, producing unbiased estimates as long as observations are missing at random. This allows the use of all available data from all subjects, thereby minimizing the effects of loss to follow-up. To make the most efficient use of our data we will fit a single model using all time points for each outcome. Our specific aims and hypotheses correspond to specific contrasts within those models. Demographic variables (e.g., age, gender, etc.) and variables characterizing the course of depressive symptoms (e.g., age of onset, chronicity, number of episodes, length of the current episode, etc.) will be compared by treatment group and examined in relation to outcome variables; this would define one possible set of appropriate covariates, if needed.

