Aim 1: Primary analysis: Our primary analysis will consist of a GLMM for HAMD-24 with treatment group effects and time main effects, along with two-way interactions of time and group. The primary analysis will assess treatment effects at the end of treatment at 12 weeks. Our primary analysis is valid under the assumption of missing-at-random. To study missingness patterns, we will compare mean response trajectories of the primary outcome measure HAMD for subjects who dropped out and those who did not. We will further compare treatment groups for drop-out rates, time to drop-out and drop-out reasons. Since it is theoretically impossible to rule out data missing-not-at-random, we will also perform sensitivity analysis taking a pattern mixture approach. Our pattern mixture approach will make assumptions on how the outcome trajectory

for subjects who dropped out will differ from those for subjects who did not. These differences will be allowed to be vary across treatment arms and the amount of difference will be varied in a plausible range to obtain a full sensitivity analysis.

Secondary analysis: Treatment maintenance will be assessed via the GLMM at follow-up as part of the secondary analysis. Secondary analysis will also include comparison of remission status (binary outcome) at the end of treatment between treatment groups via a logistic regression. Analyses for secondary outcomes clinical global improvement (CGI) and cognitive domain scores in the executive function and memory domains will be similar to those above for the continuous HAMD scores. As noted in the Neuropsychological Assessment section, there are 4 cognitive domains that are being assessed. Of these, the two primary cognitive domains of interest for this proposal are executive function and memory. A separate GLMM as above will be estimated using these 2 domain scores as dependent variables. In addition treatment adherence and time in practice will be considered as moderators of treatment effects in the longitudinal modeling of primary depression and imaging outcomes in the first two aims.

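### Remission is analysed at week 12 only, by a logistic regression with no stated missing-data rule or covariates, although worsening can end participation and two-weekly HAMD scores are available

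*Combined protocol and SAP*

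**What the plan says.** Section 9.6 states a general principle for the longitudinal analyses: "To make the most efficient use of our data we will fit a single model using all time points for each outcome". It gives as a benefit: "This allows the use of all available data from all subjects, thereby minimizing the effects of loss to follow-up". For HAMD it adds a missing-at-random assumption, a comparison of dropout between arms, and a pattern-mixture sensitivity analysis (repeated in section 10.3.5). CGI and the cognitive domain scores are to be analysed in the same way as HAMD.

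Remission is treated separately, in the Aim 1 secondary analysis: "comparison of remission status (binary outcome) at the end of treatment between treatment groups via a logistic regression". Nothing further is said about covariates, missing status or sensitivity analysis for this outcome. Section 9.6 mentions possible demographic and illness-course covariates in general terms, to be used if needed, but ties none to remission.

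Two other statements bear on this:

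- Section 9.4 (and section 7.3 in the same terms) says that on "worsening of their depressive symptoms by week 12 (i.e., CGI-I score > 4) of treatment, they will be discontinued from the study".
- Section 9.6 says that "HAMD-24 scores will be recorded every 2 weeks throughout the intervention", so a subject who leaves early will usually have interim scores.

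**The concern.** A logistic regression with one record per subject uses only subjects whose outcome is known. With no rule for the others, statistical software leaves them out. If subjects leave because they are doing badly, those who remain are a favourable selection and remission is overstated in both arms. If leaving is more common in one arm, the comparison between arms is distorted as well.

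The HAMD mixed model reduces this problem because it uses the interim scores that precede dropout. The remission analysis discards them.

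The silence also leaves room for choice after the data are seen. Excluding such subjects, counting them as not remitted, and carrying in an early-termination score are all compatible with the text, and they can give different rates. Remission is the first secondary outcome listed in section 9.5.2, and section 2.1 says the trial should supply effect sizes for future studies, so a biased rate could be carried forward.

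**Working it through.** **Inputs from the documents.** 220 subjects, 1:1, so 110 per arm (9.6). At most 10% dropout by week 12, so 220 × 0.9 / 2 = 99 per arm (Sample Size and Population; 9.2). Seven HAMD visits, correlation 0.5, d = 0.32 (9.2). Pilot effect 0.65 (9.2). Remission of 30–35% in antidepressant trials in older adults (2.2).

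**Assumptions.** Two-sided α of 0.05. HEW remission equals that 30–35%, because no arm-specific rate is given. HAMD is normal with equal correlation.

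**1. The plan's own figure.** Section 9.2 claims "80% power at significance level $\alpha=0.05$ for detecting a treatment and time interaction", with "no difference at baseline and a difference of $d = 0.32$ SDs between any two arm at the end follow-up". With time scaled from 0 to 1 over seven equally spaced visits, Sxx = 28/36 = 0.778. Then SE = √[2(1 − 0.5)/(99 × 0.778)] = 0.114, 0.32/0.114 = 2.81, and power = Φ(2.81 − 1.96) = 80.2%. The figure reproduces. No power is stated for remission.

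**2. Remission with full data.** A shift of 0.32 SD moves 30% to Φ(−0.524 + 0.32) = 41.9%, an odds ratio of (0.419/0.581)/(0.30/0.70) = 1.68. The two-proportion formula gives 45% power with 110 per arm and 41% with 99.

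**3. Dropout driven by interim HAMD.** In a simulation, a subject left once a score at weeks 2–10 exceeded the expected HEW mean at that visit by a fixed amount. The amount was set so that 10% left overall. The same trigger in both arms gave 8.5% dropout in TCC and 11.5% in HEW at d = 0.32. Rates and log odds ratios come from 200,000 subjects per arm; power comes from 800 trials of 110 per arm.

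| HEW rate | True TCC / HEW | Observed cases only | Log OR, true / observed | Power: full / observed / imputed |
|---|---|---|---|---|
| 30% | 42.0 / 30.2% | 45.2 / 33.5% | 0.515 / 0.492 | 45 / 40 / 44% |
| 35% | 47.4 / 35.0% | 51.0 / 38.8% | 0.516 / 0.494 | 46 / 41 / 46% |

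The log odds ratio is low by 1 − 0.492/0.515 = 4.5% and 1 − 0.494/0.516 = 4.3%. Imputed means multiple imputation of week-12 HAMD from arm and earlier scores. Counting leavers as not remitted gave a log odds ratio of 0.513 in both rows, because only 4 to 9% of them would have remitted. With no treatment effect, rejection stayed near 5% for every method. At the pilot effect of 0.65 with 30% in HEW, power was 93% on observed cases and 96% with imputation.

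**4. Dropout that differs by arm.** Suppose every leaver is a non-remitter. The observed rate is then p/(1 − dropout). With 30% against 41.9%:

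| Dropout TCC / HEW | Observed TCC / HEW | Odds ratio (true 1.68) |
|---|---|---|
| 10 / 10% | 46.6 / 33.3% | 1.74 |
| 5 / 15% | 44.1 / 35.3% | 1.45 |
| 15 / 5% | 49.3 / 31.6% | 2.11 |

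With 35% in HEW and 47.4% in TCC (true 1.67) the same splits give 1.75, 1.42 and 2.16.

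**5. Dependence on the mechanism.** If the trigger is change from baseline instead of current level, the bias disappears in this model. Under equal correlation, Cov(Yt − Y0, Y12) = 0.5 − 0.5 = 0, so leaving carries no information about the week-12 score.

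**The case against.** A reader might infer that the plan excludes subjects without a week-12 score. The documents do not say so, and several sections point the other way:

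- Section 9.3 defines the ITT set as all randomised subjects with a baseline assessment.
- Section 9.5 schedules outcome measures on early termination.
- Sections 2.2, 5.4 and 8 keep observing people who stop the intervention.
- A subject who first meets the worsening rule at the week-12 visit already has a score.

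This stands: the defect is a missing rule, not a stated exclusion. But these sections do not supply the rule. The ITT definition does not say what status a subject without week-12 data receives. An early-termination score may come from week 4, and the plan does not say whether it counts as week 12. Section 2.2 concerns the post-intervention follow-ups, and section 8 invites those who worsen to months 6 and 12, so neither guarantees a week-12 score.

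A reader might also infer that the excluded are mostly non-remitters, or that the arm difference always shrinks. Section 9.4 lists six dropout reasons with no expected split, and the direction is not fixed, as steps 4 and 5 show.

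Finally, remission is a secondary outcome with no power claim. The HAMD analysis has its own missing-data handling, and dropout is to be compared between arms by rate, timing and reason, so an imbalance would be noticed. That limits the stakes. It does not say how remission should then be analysed.

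**Conclusion.** The point holds as a gap in the specification. The remission analysis departs from the all-visits principle of section 9.6 and has no missing-data rule, in a trial whose own discontinuation rule plausibly links missingness to outcome.

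At the planned 10% dropout the effect is modest: arm rates about 3 to 4 points too high, the log odds ratio 4 to 5% too small, and 4 to 5 points of power lost against imputation. This rests on 30–35% HEW remission, d = 0.32, correlation 0.5 and a trigger on current HAMD level. It becomes material if dropout differs clearly by arm. The odds ratios of 1.45 and 2.11 are bounding illustrations, since they assume that no leaver would have remitted.

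The documents do not support a claim that the treatment effect is biased in one particular direction, that type I error is inflated when the dropout mechanism is the same in both arms, or that the primary HAMD analysis is affected. The supplied text gives no numerical definition of remission; part of the front matter was not available, so this is not counted as a fault. The change is a minor but worthwhile improvement.

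**What to change.** In section 9.6, specify the remission analysis on the ITT set of section 9.3:

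1. Multiply impute week-12 HAMD from arm and all two-weekly scores under missing at random, the assumption already made for HAMD.
2. Apply the trial's remission definition to the completed data.
3. Fit the logistic regression adjusted for baseline HAMD and the randomisation strata (site and imaging, section 6.2.2), and combine the results across imputations. Report the arm rates too, because an adjusted odds ratio is not directly comparable with an unadjusted one.

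A logistic GLMM over all visits, with the week-12 contrast, is an acceptable alternative and closer to the principle in section 9.6.

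Add a sensitivity analysis that counts subjects without a week-12 score as not remitted. State whether an early-termination score counts as week 12. Sections 7.3 and 9.4, which discontinue subjects from the study, must be reconciled with sections 2.2, 5.4 and 8, which continue to follow them, so that it is clear who will have a week-12 assessment.

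The cost is a few lines of SAP text and a standard imputation step. No new data are needed.

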1.2 Secondary Objectives

Aim 2. To test whether 12 weeks of **TCC** compared to **HEW** training alter neural regulation of affect during an fMRI affect labeling task and functional connectivity in older adults with depressive symptoms. Imaging biomarkers will predict/moderate treatment response.

Hypothesis 2a: Compared to HEW, TCC will lead to improved functional connectivity in the Default Mode Network as measured with resting state (rs-) fMRI;

Hypothesis 2b: Compared to **HEW**, **TCC** will result in greater activation in the anterior cingulate;

Hypothesis 2c: Imaging biomarkers (hippocampal and anterior cingulate volume, white matter hyperintensity and DMN connectivity) will moderate and predict 1) rate of improvement in symptoms and function; and 2) improvement in cognitive performance.

Aim 3. To examine whether older depressed participants with MCI (LLD+MCI) differ in their cognitive trajectory and neural circuitry compared to older depressed participants without MCI (LLD-MCI) at extended follow-up of 6 and 12 months.

Hypothesis 3a: We hypothesize that changes in episodic memory and executive function will be greater in those with LLD+MCI than in those with LLD-MCI.

Hypothesis 3b: We hypothesize that changes in the default mode/hippocampal-frontal network and in the executive-control and cortico-limbic circuitry will be greater in those with LLD+MCI than in those with LLD-MCI.

Aim 4. *To examine whether greater degradation of neural circuitry is associated with greater cognitive decline.*

Hypothesis 4: We hypothesize that changes in default mode/hippocampal-frontal network and executive-control and cortico-limbic circuitry will be associated with decline in episodic memory and executive function.

Exploratory Aim 1: We will explore the role of treatment-resistance or poor response to the intervention in predicting cognitive outcomes.

Exploratory Aim 2: We will follow a subset of participants (those recruited within 2 years of the initial evaluation) to assess clinical trajectory of mood and cognitive symptoms with 24-month follow-up.

Exploratory aim 3: We will explore the difference in changes in gene expression and peripheral pro-inflammatory cytokines associated with clinical response to the interventions. To use peripheral blood to conduct transcriptome profiling with the same R01 protocols to identify gene expression and peripheral inflammatory biomarkers correlates of clinical response to TCC versus HEW.

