Exploratory Hypothesis 2c: Exploratory analysis: Exploratory variables will include hippocampal and anterior cingulate volume and white matter high intensity. To test hypotheses about the relationships between the imaging metrics and the primary outcomes in mood and cognition, we will derive domain summary scores for the 2 cognitive domains of interest, memory, and executive function. We will assess treatment moderator effects of baseline hippocampal and anterior cingulate volume and white matter high intensity on HAMD and memory and executive function domain scores. Statistical evaluation of moderators will be done by including the posited moderator variable as an independent variable and evaluating the moderator x treatment group interaction term in the GLMM models proposed in Aim 1. In addition we will assess the treatment mediator effects of change in DMN connectivity on change in HAMD and memory and executive function domain scores. Mediation effects will be assessed via multiple regression models, where the posited mediator variable is regressed on treatment, outcome is regressed on treatment and the outcome is regressed on the mediator and the treatment. For confirmation of the mediation effect, treatment effects need to be found significant on the outcome and the mediator as well as a decreased treatment effect size on the outcome in the presence of the mediator.

Exploratory aim 1: We will explore the difference in changes in gene expression and peripheral pro-inflammatory cytokines associated with clinical response to the interventions, by comparing the change in these markers between the two intervention groups and by examining how the change in these markers correlate with changes in depression and cognitive scores in the two groups.

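### As written, the exploratory Hypothesis 2c moderator test leaves time out of the tested term, so it estimates a visit-averaged arm difference and not moderation of the week-12 effect or of the speed of improvement

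*Combined protocol and SAP*

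**What the plan says.** Section 9.6 (Exploratory Hypothesis 2c) enters each moderator as an independent variable and tests it by "evaluating the moderator x treatment group interaction term in the GLMM models proposed in Aim 1". The moderators named there are baseline hippocampal volume, anterior cingulate volume and white matter hyperintensity. The outcomes are HAMD and the memory and executive function scores, which makes 3 x 3 = 9 tests.

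The Aim 1 model is "a GLMM for HAMD-24 with treatment group effects and time main effects, along with two-way interactions of time and group". Section 9.6 also says that "we will fit a single model using all time points for each outcome".

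Section 9.2 counts baseline among the HAMD responses, "7 time points (baseline, 2, 4, 6, 8, 10, 12 weeks", and states power "for detecting a treatment and time interaction corresponding to no difference at baseline".

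The hypothesis in Section 1.2 is that the imaging biomarkers "will moderate and predict 1) rate of improvement in symptoms and function". No moderator x time or moderator x group x time term appears anywhere, and no power is stated for the moderator tests.

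**The concern.** In this model the treatment effect is the group x time interaction: the arms start equal and separate. A variable that modifies that effect therefore acts through moderator x group x time. If only moderator x group is added, its coefficient has no time index. It is the difference between arms in the moderator's association with the outcome, averaged over every visit in the model. Baseline is one of those visits, and randomisation makes the expected interaction there zero.

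At stake is the meaning of the nine moderator results. The coefficient's relation to week-12 moderation depends on how many visits are modelled and on how the effect develops, so it cannot be read as either quantity the hypothesis needs. The part of 2c about predicting improvement has no stated test either, because that needs a moderator x time term.

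**Working it through.** **Inputs.** Section 9.2: 7 visits (baseline to week 12), correlation 0.5 between any two visits, growth "if the treatment main effects are linear over the 12 week treatment phase on HAMD", 80% power, alpha 0.05 (taken as two-sided), 99 complete per arm. Section 6.2.1: 55 per arm with imaging. Appendix A: HAMD also at months 4, 5, 6 and 12. Section 6.2: cognition at baseline, week 12, 6 months and 12 or 24 months (weeks 0, 12, 24 and 52 used below). Outcome SD and moderator SD are set to 1. Compound symmetry is assumed.

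**The plan's own figure.** With time scaled 0 to 1 in sixths, Sxx = 28/36 = 0.778. The slope variance is (1 - 0.5)/0.778 = 0.643. The detectable difference is 2.80 x sqrt(2 x 0.643/99) = 0.319, which matches the stated 0.32. A week-12 change contrast would give 0.398 and a baseline-adjusted endpoint 0.345. Of the variants tried, only the slope test reproduces the plan's figure, so the plan does place the treatment effect in the time interaction.

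**Signal per unit of week-12 moderation (7 visits, linear, correlation 0.5).**
- Two-way term: mean effect 0.5, variance (1 + 6 x 0.5)/7 = 0.571, signal 0.5/sqrt(0.571) = 0.661.
- Three-way week-12 contrast: variance 2 x (1 - 0.5) = 1, signal 1.000.
- Three-way linear slope: variance 0.643, signal 1/sqrt(0.643) = 1.247.

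**Power of the two-way term where the comparator has 80%** (2.80 standard errors):
- Against the week-12 contrast: 2.80 x 0.661 = 1.853, and Phi(1.853 - 1.960) = 46%.
- Against the slope: 2.80 x 0.661/1.247 = 1.486, and Phi(1.486 - 1.960) = 32%.

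These ratios do not depend on n. With 55 per arm, the slope test has 80% power for 2.80 x sqrt(2 x 0.643/55) = 0.43 SD at week 12 per SD of moderator. In 400 simulated mixed-model fits at that value, the two-way term averaged 0.217 with 34% power and the three-way slope term 0.433 with 78%.

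**Other visit sets and trajectories** (coefficient as a fraction of the full effect, then two-way power where the comparator has 80%):

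| Outcome and trajectory | Comparator | Fraction | corr. 0.3 | corr. 0.5 | corr. 0.7 |
|---|---|---|---|---|---|
| HAMD, 7 visits, linear | week-12 contrast | 0.50 | 75% | 46% | 24% |
| HAMD, 7 visits, linear | slope | 0.50 | 56% | 32% | 17% |
| HAMD, 11 visits, linear to week 12, then plateau | week-12 contrast | 7.5/11 = 0.68 | 96% | 73% | 41% |
| HAMD, 7 visits, full effect from week 2 | week-12 contrast | 6/7 = 0.86 | 99% | 89% | 58% |
| Cognition, baseline and week 12 only | week-12 contrast | 0.50 | 54% | 37% | 22% |
| Cognition, 4 visits, full effect by week 12, held | week-12 contrast | 0.75 | 95% | 76% | 46% |
| Cognition, 4 visits, linear to month 12 | slope | 0.42 | 49% | 30% | 17% |

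In the last row the full effect is the month-12 effect and the fraction is (0 + 12 + 24 + 52)/(4 x 52) = 0.423. The week-12 effect in that row is 12/52 = 0.231 of the month-12 effect, so there the two-way coefficient exceeds week-12 moderation. The term can fall below or above the target.

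**The case against.** The strongest defence is that the wording is shorthand. Section 9.6 refers to the Aim 1 models, whose treatment effect is assessed at week 12, and says that hypotheses correspond to contrasts within those models. The opening of Section 9 describes adherence in the same way, through interactions with treatment, and the Aim 2 text shows that the authors read interactions with time as differing trajectories. The intention may well be sound. But no contrast is given for moderation, and the term that is named is not the one needed.

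Section 9.5.1 defines the primary outcome as change in HAMD. If change scores were the response, baseline would no longer dilute the estimate. However, Sections 9.2 and 9.6 model HAMD-24 itself with baseline as a time point, and the cognitive outcomes are domain scores. Even with change scores, the term would be change averaged over visits.

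Three stronger readings are tempting and are not supported:
- A reader might infer that true moderators will generally be missed, or that power simply falls to 32%. That figure is one scenario measured against a slope test. The table shows no loss in some settings and a gain with an early, sustained effect, and the plan claims no power for these tests.
- A reader might infer that chance baseline imbalance is a special weakness of the two-way term. For a chance baseline interaction b at correlation 0.5, the average shifts by (b + 6 x 0.5b)/7 = +0.57b and the change contrast by 0.5b - b = -0.50b. The two are similar in size.
- A reader might infer that the main conclusions are at risk. Section 9.6 labels this analysis exploratory, and the Aim 1 primary and Aim 2 co-primary analyses do not use the term.

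**Conclusion.** The point holds as an estimand error in the literal text. With baseline among the responses, moderator x group without time is a visit-averaged quantity and does not answer Hypothesis 2c. That conclusion needs no numerical assumption.

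The size of the power consequence does need assumptions. On the plan's 7-visit, linear, correlation-0.5 inputs, the coefficient is half the week-12 moderation and power is 46% against an 80% week-12 contrast. With 11 HAMD visits and a plateau it is about 73%, and for cognition over four visits about 30% to 76% at correlation 0.5, the lower figure being against a 12-month slope test. All figures assume complete data and compound symmetry; Section 9.2 leaves the covariance structure to be selected later.

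This is worth correcting before analysis, but it is not a must-fix for the trial's main conclusion.

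**What to change.** In Section 9.6, Exploratory Hypothesis 2c, state that moderator, moderator x group, moderator x time and moderator x group x time are added to the Aim 1 models. Define moderation as the moderator x group x time contrast from baseline to week 12, for HAMD and for the memory and executive function scores.

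For the prediction part of 2c, use the moderator x time contrast averaged over arms (group centred), or take it from a model without the three-way term. With an uncentred group indicator and the three-way term present, moderator x time describes the reference arm only.

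The cost is a few lines of SAP text and two further interactions per model. No new data are needed. Settling this before analysis also removes a later choice between two-way and three-way results.
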